### 4.3.1.3 Rescue Medications and Supportive Care for Pembrolizumab

#### Supportive Care Guidelines

Patients should receive appropriate supportive care measures as deemed necessary by the treating investigator. Suggested supportive care measures for the management of adverse events with potential immunologic etiology are outlined below. Where appropriate, these guidelines include the use of oral or intravenous treatment with corticosteroids as well as additional anti-inflammatory agents if symptoms do not improve with administration of corticosteroids. Note that several courses of steroid tapering may be necessary as symptoms may worsen when the steroid dose is decreased. For each disorder, attempts should be made to rule out other causes, such as metastatic disease or bacterial or viral infection, which might require additional supportive care. The treatment guidelines will be applied when the investigator determines the events to be related to pembrolizumab.

**Note:** if after the evaluation the event is determined not to be related, the investigator does not need to follow the treatment guidance (as outlined below). Refer to Section 4.3.1.2 for dose modifications.

It may be necessary to perform conditional procedures, such as bronchoscopy, endoscopy, or skin photography as part of evaluation of the event.

- **Pneumonitis:**
  - For **Grade 2 events**, treat with systemic corticosteroids. When symptoms improve to Grade 1 or less, steroid taper should be started and continued over no less than 4 weeks.
  - For **Grade 3-4 events**, immediately treat with intravenous steroids. Administer additional anti-inflammatory measures, as needed.
  - Add prophylactic antibiotics for opportunistic infections in the case of prolonged steroid administration.
  
- **Diarrhea/Colitis:**

Subjects should be carefully monitored for signs and symptoms of enterocolitis (such as diarrhea, abdominal pain, blood or mucus in stool, with or without fever) and of bowel perforation (such as peritoneal signs and ileus).

  - All subjects who experience diarrhea/colitis should be advised to drink liberal quantities of clear fluids. If sufficient oral fluid intake is not feasible, fluid and electrolytes should be substituted via IV infusion. For Grade 2 or higher diarrhea, consider GI consultation and endoscopy to confirm or rule out colitis.
  - For **Grade 2 diarrhea/colitis** administer oral corticosteroids.
  - For **Grade 3 or 4 diarrhea/colitis**, treat with intravenous steroids followed by high dose oral steroids.

- When symptoms improve to Grade 1 or less, steroid taper should be started and continued over no less than 4 weeks.
- **Type 1 diabetes mellitus (if new onset, including diabetic ketoacidosis [DKA]) or  $\geq$  Grade 3 Hyperglycemia, if associated with ketosis (ketonuria) or metabolic acidosis (DKA)**
  - For **T1DM** or **Grade 3-4** Hyperglycemia
    - Insulin replacement therapy is recommended for Type I diabetes mellitus and for Grade 3-4 hyperglycemia associated with metabolic acidosis or ketonuria.
    - Evaluate patients with serum glucose and a metabolic panel, urine ketones, glycosylated hemoglobin, and C-peptide.
- **Hypophysitis:**
  - For **Grade 2** events, treat with corticosteroids. When symptoms improve to Grade 1 or less, steroid taper should be started and continued over no less than 4 weeks. Replacement of appropriate hormones may be required as the steroid dose is tapered.
  - For **Grade 3-4** events, treat with an initial dose of IV corticosteroids followed by oral corticosteroids. When symptoms improve to Grade 1 or less, steroid taper should be started and continued over no less than 4 weeks. Replacement of appropriate hormones may be required as the steroid dose is tapered.
- **Hyperthyroidism or Hypothyroidism:**

Thyroid disorders can occur at any time during treatment. Patients should be monitored for changes in thyroid function (at the start of treatment, periodically during treatment, and as indicated based on clinical evaluation) and for clinical signs and symptoms of thyroid disorders.

  - **Grade 2** hyperthyroidism events (and **Grade 2-4** hypothyroidism):
    - In hyperthyroidism, non-selective beta-blockers (e.g. propranolol) are suggested as initial therapy.
    - In hypothyroidism, thyroid hormone replacement therapy, with levothyroxine or liothyronine, is indicated per standard of care.
  - **Grade 3-4** hyperthyroidism
    - Treat with an initial dose of IV corticosteroid followed by oral corticosteroids. When symptoms improve to Grade 1 or less, steroid taper should be started and continued over no less than 4 weeks. Replacement of appropriate hormones may be required as the steroid dose is tapered.

- **Hepatic:**
  - For **Grade 2** events, monitor liver function tests more frequently until returned to baseline values (consider weekly).
    - Treat with IV or oral corticosteroids
  - For **Grade 3-4** events, treat with intravenous corticosteroids for 24 to 48 hours.
  - When symptoms improve to Grade 1 or less, a steroid taper should be started and continued over no less than 4 weeks.
  
- **Renal Failure or Nephritis:**
  - For **Grade 2** events, treat with corticosteroids.
  - For **Grade 3-4** events, treat with systemic corticosteroids.
  - When symptoms improve to Grade 1 or less, steroid taper should be started and continued over no less than 4 weeks.
  
- **Steven's Johnson Syndrome (SJS) and Toxic Epidermal Necrolysis (TEN)**
  - For signs and symptoms of SJS or TEN, withhold pembrolizumab and refer the patient for specialized care for assessment and treatment
  - If SJS or TEN is confirmed, permanently discontinue pembrolizumab
  
- **Immune-mediated myocarditis management**
  - For suspected immune-mediated myocarditis, ensure adequate evaluation to exclude other etiologies and administer corticosteroids as appropriate
  
- **Infusion Reaction:**

See section 4.3.1.1

#### 4.4 Concomitant Medications/Treatments

Medications or vaccinations specifically prohibited in the exclusion criteria provided in section 3.2 are not allowed during the ongoing trial. If there is a clinical indication for one of these or other medications or vaccinations specifically prohibited during the trial, discontinuation from trial therapy or vaccination may be required. The investigator should discuss any questions regarding this with the Merck Clinical team. The final decision on any supportive therapy or vaccination rests with the investigator and/or the subject's primary physician.

##### 4.4.1 Acceptable Concomitant Medications

All treatments that the investigator considers necessary for a subject's welfare may be administered at the discretion of the investigator in keeping with the community standards of medical care.

All concomitant medication will be recorded on the case report form (CRF) including all prescription, over-the-counter (OTC), herbal supplements, and IV medications and fluids. If changes occur during the trial period, documentation of drug dosage, frequency, route, and date may also be included on the CRF.

All concomitant medications received within 28 days before the first dose of drug treatment and 30 days after the last dose of pembrolizumab should be recorded. Concomitant medications administered within 30 days after the last dose of pembrolizumab treatment should be recorded for SAEs and events of clinical interest (ECIs) as defined in Section 7.3.3.

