#### 6.4 Long-term follow up (90 days after week 12 dose of pembroluzimab)

Clinical evaluation: focused history on symptoms/toxicity.

Toxicity: Per NCI CTCAEv4.03; Serious adverse events (SAEs; or follow-up to any SAEs) that occur within 90 days of the end of pembrolizumab (or prior to start of new anti-cancer therapy, whichever is earlier) or any grade of Events of Clinical Interest (see section 7.3) that occur within 90 days of the end of pembrolizumab or 30 days after the initiation of a new anti-cancer therapy (whichever is earlier) must be recorded.

Survival analysis:

**Note:** Subsequent follow-up visits to occur every 90 days ( $\pm$  15 days) for up to 3 years or until death (whichever is first) may be conducted via telephone or chart review, and will be limited to history, date of progression on or following pembrolizumab therapy, if any subsequent cancer treatments were given, an assessment of any SAE's considered to be possibly or probably related to study treatment until resolution, and survival status.

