### 7.1.2 Suspected Adverse Reaction (SAR)

A suspected adverse reaction (SAR) is any AE for which there is a *reasonable possibility* that the drug is the cause. *Reasonable possibility* means that there is evidence to suggest a causal relationship between the drug and the AE. A suspected adverse reaction implies a lesser degree of certainty about causality than adverse reaction, which means any adverse event caused by a drug.

Causality assessment to a study drug is a medical judgment made in consideration of the following factors: temporal relationship of the AE to study drug exposure, known mechanism of action or side effect profile of study treatment, other recent or concomitant drug exposures, normal clinical course of the disease under investigation, and any other underlying or concurrent medical conditions. Other factors to consider in considering drug as the cause of the AE:

- Single occurrence of an uncommon event known to be strongly associated with drug exposure (e.g., angioedema, hepatic injury, Stevens-Johnson Syndrome)
- One or more occurrences of an event not commonly associated with drug exposure, but otherwise uncommon in the population (e.g., tendon rupture); often more than once occurrence from one or multiple studies would be needed before the sponsor could determine that there is *reasonable possibility* that the drug caused the event.
- An aggregate analysis of specific events observed in a clinical trial that indicates the events occur more frequently in the drug treatment group than in a concurrent or historical control group

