### 7.3 SAEs or Serious SARs

#### 7.3.1 Timing

After informed consent but prior to initiation of study medications, only SAEs caused by a protocol-mandated intervention will be collected (e.g. SAEs related to invasive procedures such as biopsies, medication washout).

For any other experience or condition that meets the definition of an SAE or a serious SAR, recording of the event must begin from day 1 of study treatment and continue through the 90-day follow-up period after treatment is discontinued (or to the initiation of new anti-cancer treatment, whichever is earliest).

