### 7.3.3.1 Merck Reporting Requirements:

For the time period beginning when the consent form is signed until treatment allocation/randomization, any serious adverse event, or follow up to a serious adverse event, including death due to any cause other than progression of the cancer under study that occurs to any subject must be reported within 24 hours to the Sponsor and within 2 working days to Merck Global Safety if it causes the subject to be excluded from the trial, or is the result of a protocol-specified intervention, including but not limited to washout or discontinuation of usual therapy, diet, placebo treatment or a procedure.

For the time period beginning at treatment allocation/randomization through 90 days following cessation of treatment, or 30 days following cessation of treatment if the subject initiates new anticancer therapy, whichever is earlier, any serious adverse event, or follow up to a serious adverse event, including death due to any cause other than progression of the cancer under study whether or not related to the Merck product, must be reported within 24 hours to the Sponsor and within 2 working days to Merck Global Safety.

Additionally, any serious adverse event, considered by an investigator who is a qualified physician to be related to Merck product that is brought to the attention of the investigator at any time following consent through the end of the specified safety follow-up period specified in the paragraph above, or at any time outside of the time period specified in the previous paragraph also must be reported immediately to the Sponsor and to Merck Global Safety.

All subjects with serious adverse events must be followed up for outcome.

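### Section 4.4.1 ends medication recording for SAEs and ECIs at 30 days after the last dose, although those events are collected for up to 90 days

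*Combined protocol and SAP*

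**What the plan says.** **Medication recording.** Section 4.4.1 first sets a general window: "All concomitant medications received within 28 days before the first dose of drug treatment and 30 days after the last dose of pembrolizumab" are to be recorded. The next sentence addresses SAEs and ECIs: "Concomitant medications administered within 30 days after the last dose of pembrolizumab treatment should be recorded for SAEs and events of clinical interest (ECIs"). Both windows end 30 days after the last dose.

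**Event collection.** Section 7.3.1 has SAE recording start on day 1 of treatment and "continue through the 90-day follow-up period after treatment is discontinued", or until new anti-cancer treatment begins if that is sooner. Section 6.4 and footnote 4 of the Time and Events Table require SAEs and ECIs "that occur within 90 days of the end of pembrolizumab" to be recorded, again with cut-offs for new therapy. Section 7.3.3.1 requires SAEs and ECIs to be reported to the funder "through 90 days following cessation of treatment, or 30 days following cessation of treatment if the subject initiates new anticancer therapy".

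**Visits.** The Time and Events Table marks concomitant medications at screening, on day 1 of cycles 1 to 4 and at end of study treatment. The long-term follow-up cell is empty. Section 6.4 lists no medication review for that visit.

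**Use of the data.** Section 7.1.2 names "other recent or concomitant drug exposures" among the factors to weigh when judging whether the study drug caused an event.

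**The concern.** A separate sentence for SAEs and ECIs has a purpose only if it asks for more than the general rule. Here it asks for a subset of what the general rule already covers. The event windows run well past it, so the log that should support the assessment of a late event can close before the event occurs.

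Three features of the protocol make later drug exposure relevant:

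- Section 4.4.2 prohibits no therapy in post-treatment follow-up, so other drugs may be started just when recording stops.
- One of the two ECIs listed in Section 7.3.3.1 is a pattern of abnormal liver tests, which the protocol says may call for a search for the underlying cause. Other drugs are an obvious candidate.
- Section 4.3.1.2 expects that immune-related events may appear several months after the last dose, and Section 4.3.1.3 describes steroid tapers of at least four weeks. Steroids given for an event arising after day 30 need not be entered.

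At stake is the completeness and consistency of the safety record for late events, including at affiliate sites that enter their own data (Section 9.4).

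**Working it through.** The plan states no figure for this gap. The check is a comparison of windows, counted in days after the last pembrolizumab dose.

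**Inputs**

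| Item | End of window | Source |
|---|---|---|
| All concomitant medications | day 30 | 4.4.1, first window sentence |
| Concomitant medications for SAEs and ECIs | day 30 | 4.4.1, second window sentence |
| SAE recording | day 90, or start of new anti-cancer therapy | 7.3.1; 6.4; footnote 4 |
| ECI recording | day 90, or 30 days after start of new therapy | 6.4; footnote 4 |
| SAE and ECI reporting to the funder | day 90, or day 30 if new therapy starts | 7.3.3.1 |

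**Step 1: does the SAE/ECI sentence extend the general rule?** Both end on day 30. Days added: 30 − 30 = 0.

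**Step 2: the gap when no new anti-cancer therapy starts.** Event window minus medication window: 90 − 30 = 60 days (days 31 to 90). As a share of the post-treatment event window: 60 / 90 = 67%.

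**Step 3: the gap when new therapy starts on day d, with d between 30 and 90.**
- SAE recording under 7.3.1 closes on day d, so the gap is d − 30, which is less than 60.
- ECI recording under 6.4 closes on day 90 or day d + 30, whichever is earlier. The gap is the smaller of 60 and d.
- Reporting under 7.3.3.1 closes on day 30, so the gap is 30 − 30 = 0.

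The gap is therefore up to 60 days, not 60 days for every patient.

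**Step 4: does a scheduled visit cover the interval?** The end-of-treatment visit, where medications are reviewed, falls 30 ± 7 days after the last dose (days 23 to 37; Section 4.6). If it is held as day 1 of cycle 5, it falls about 21 days after the cycle 4 dose. The first long-term follow-up visit is at 90 ± 15 days (days 75 to 105; Section 4.7) and has no medication review.

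**Step 5: does other text fill the gap?**
- An undated sentence in 4.4.1 says that concomitant medication goes on the CRF, but the following paragraph sets the 30-day limit.
- Follow-up visits capture subsequent cancer treatments (4.7, 6.4, footnote 4), but no other drugs.
- MedWatch documents (7.3.3, Process) apply to events already deemed serious, suspected and unexpected. They therefore come after the causality judgement.

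**After the change in the fix.** With the medication window equal to the event window, the gap is 90 − 90 = 0 days.

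**The case against.** The strongest reply is that Section 4.4.1 governs CRF entries, not what the investigator may know. Section 7.1.2 calls causality a medical judgement and lists factors to consider. It does not confine the investigator to the CRF. SAEs go into a separate console within 24 hours (Section 7.3.2); its fields are not in the documents, so it cannot be said to omit drugs. Drugs logged up to day 30 remain available for a later event. Patients with an ongoing SAE or an adverse event of grade 2 or higher are followed to resolution (Section 4.6). All of this stands. A reader might infer that late events have no drug information at all, or that FDA reports will lack it. The documents do not support that. What is missing is a required CRF record.

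A reader might also size the gap by the onset times in Section 5.1.6, such as medians of 3.5 months for hypothyroidism and 5 months for pneumonitis. That comparison does not hold. The ECIs listed in 7.3.3.1 are overdose and the liver-test pattern, and non-serious events are documented only to 30 days (Section 7.2). A typical non-serious case on days 31 to 90 would thus not be a collected SAE or a listed ECI, although Section 6.6 speaks more broadly of immune-related ECIs. Patients who benefit may also continue pembrolizumab as standard care, which moves the last dose.

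Finally, a medication log shorter than the SAE window can be a deliberate economy, and no analysis in Section 8 uses concomitant medications. That limits the weight of the point. It does not explain a sentence written for SAEs and ECIs that has no effect.

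**Conclusion.** The inconsistency is real and lies in the current text. For an SAE or ECI first arising on days 31 to 90, up to 60 of the 90 days, the protocol requires no CRF record of concomitant drugs other than subsequent cancer treatments, although it names such exposures as a causality factor.

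This rests on two assumptions: that the window in 4.4.1 overrides the undated sentence before it, and that no CRF or SAE-console instruction outside the documents asks for these drugs. The documents do not say how many patients would face the full gap. Charts and SAE or MedWatch documents may partly fill it.

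The sample size, the response endpoint and the imaging analyses are unaffected. This is a safety data-collection gap that should be corrected, but it does not threaten the trial's main result.

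**What to change.** Reword the second window sentence of Section 4.4.1, for example:

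*For SAEs and ECIs, concomitant medications administered more than 30 days after the last dose of pembrolizumab should also be recorded, through the end of the SAE/ECI collection window in Sections 7.3.1 and 7.3.3.1 (90 days, or the earlier new-anti-cancer-therapy cut-off).*

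Add a matching entry, limited to SAEs and ECIs, to the long-term follow-up column of the Time and Events Table and to Section 6.4. Keep the anchor as the last dose of pembrolizumab, in line with the current sentence. Because the new-therapy cut-offs differ between 6.4, 7.3.1 and 7.3.3.1, the sentence should point to those sections and not create another cut-off.

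The cost is one sentence, one table entry and one line in Section 6.4. The 90-day visit already exists, so the only burden is slightly more data entry for the few patients with such events. The change does not reach drug-related SAEs that come to light after the window, which 7.3.3.1 makes reportable at any time.

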#### 4.4.2 Prohibited Concomitant Medications

Subjects are prohibited from receiving the following therapies during the Screening and Treatment Phase

- Anti-cancer systemic chemotherapy or biological therapy
- Immunotherapy not specified in this protocol
- Chemotherapy not specified in this protocol
- Investigational agents other than pembrolizumab
- Live vaccines within 30 days prior to the first dose of trial treatment and while participating in the trial. Examples of live vaccines include, but are not limited to, the following: measles, mumps, rubella, varicella/zoster, yellow fever, rabies, BCG, and typhoid vaccine.
- Systemic glucocorticoids for any purpose other than to modulate symptoms from an event of clinical interest of suspected immunologic etiology. The use of physiologic doses of corticosteroids may be approved after consultation with the Principal Investigator. **Note:** This does not include episodic use (up to 7 consecutive days) of systemic corticosteroids for other general conditions (e.g. pre-medication for radiographic imaging due to IV contrast allergy, COPD exacerbation, poison ivy, etc.)
- Radiation therapy
  - Note: Radiation therapy to a symptomatic solitary lesion or to the brain may be allowed at the investigator's discretion.

Subjects who, in the assessment by the investigator, require the use of any of the aforementioned treatments for clinical management should be removed from the trial. Subjects may receive other medications that the investigator deems to be medically necessary.

The Exclusion Criteria describes other medications, which are prohibited in this trial.

There are no prohibited therapies during the Post-Treatment Follow-up Phase.

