#### 4.6 End of Treatment

End of treatment visits can occur under the following circumstances:

-Patients permanently stop study treatment for disease progression or investigator/patient preference. Such visits should be performed 30 days ( $\pm 7$  days) after the last dose of pembrolizumab.

-Patients have on ongoing  $\geq$  grade 2 or serious AE (SAE). They should continue to be followed until the event is resolved or deemed irreversible by the investigator.

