6.0 EVALUATIONS AND ASSESSMENTS

6.1 Time and Events Table (After screening perform C11-AMT scan and then a research biopsy prior to Cycle 1/Day 1 of pembrolizumab)

Procedure	Screening Period 1 	Pretreatment Period 	D1 Cycle 1 	D1 Cycle 2 	D1 Cycle 3 	D1 Cycle 4 	End of Study Treatment 	Long-term Follow-up 
Informed Consent	X							
Medical History	X 							X
Physical Exam	X 		X 	X 	X 	X 	X 	
ECOG Performance Status	X		X	X	X	X	X	
CBC w/differential	X		X	X	X	X	X	
Hematology 	X		X	X	X	X	X	
INR/PT and PTT	X							
Serum chemistries 	X		X	X	X	X	X	
Liver function tests (LFTs) 	X		X	X	X	X	X	
Thyroid panel 	X				X		X	
Urine or serum pregnancy	X 		X 					
Pembrolizumab IV			X	X	X	X		
Brain MRI 	X 							
FDG PET 	X 						X	
CT scan neck chest, abdomen/pelvis 	X 						X	
AMT PET 		X						
Toxicity evaluations 	X		X	X	X	X	X	X
Fresh tumor biopsy		X						

Concomitant Medications	X		X	X	X	X	X	
Eligibility checklist	X							
Survival documentation								X

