A window of  $\pm 2$  days will apply to all study visits including treatment visits. CBC w/diff, chemistry, and LFTs on day 1, cycle 1 of pembrolizumab will be repeated only if  $>7$  days have elapsed between screening laboratory tests and day 1.

Study-related treatment with pembrolizumab is 12 weeks (or earlier if patient progresses). The end of study treatment visit should occur under the following circumstances: (1) Patients permanently stop pembrolizumab for disease progression or investigator/patient preference. Such visits should be performed 30 days ( $\pm 7$  days) after the last dose of pembrolizumab. (2) Patients who have an ongoing  $\geq$  grade 2 or serious AE (SAE) should be followed until the event is resolved or deemed irreversible by the investigator. (3) Patients who are still experiencing clinical benefit (partial response, complete response, disease stability) after 12 weeks of pembrolizumab treatment will discuss with their clinician to continue pembrolizumab as per standard of care (i.e., off study-related treatment but follow up will continue as specified in Section 6.4), especially if they are tolerating treatment well (i.e., are experiencing no ongoing SAEs), wish to continue receiving pembrolizumab.

The first long-term follow-up visit is defined as 90 days ( $\pm 15$  days) after the last dose of on-study treatment. Serious adverse events (SAEs; or follow-up to any SAEs) that occur within 90 days of the end of pembrolizumab (or prior to start of new anti-cancer therapy, whichever is earlier) or any grade of Events of Clinical Interest (see section 7.3 that occur within 90 days of the end of pembrolizumab or 30 days after the initiation of a new anti-cancer therapy (whichever is earlier) must be recorded. Subsequent follow-up visits, defined as every 3 months (90 days) thereafter ( $\pm 15$  days) for up to 3 years or until death (whichever is first) may be conducted via telephone or

chart review. These follow up visits will be limited to history of any subsequent cancer treatments, an assessment of any SAE's considered to be possibly or probably related to pembrolizumab treatment until resolution, date of disease progression on pembrolizumab, and survival status.

Complete history at baseline, physical exam to include height (baseline only), weight and vital signs (BP, respiratory rate, and temperature).

Hgb, ANC, and platelets

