Serum chemistries and electrolytes to include sodium, potassium, bicarbonate, chloride, LDH, BUN, serum creatinine, glucose, calcium, magnesium, total protein, albumin.

LFTs include total bilirubin, AST and ALT.

Thyroid panel includes TSH, T3 and free T4. This test should be performed at screening, D1 of cycle 3, and at the end of treatment.

A urine or serum pregnancy test ( $\beta$ -hCG) is required for all women of childbearing potential at screening within 14 days of the C11-AMT scan and 72 hours before the first dose of pembrolizumab.

Optimal radiographic tumor imaging for baseline clinical purposes includes whole body CT scan (chest, abdomen, and pelvis; add neck, if clinically necessary) with IV contrast coregistered with whole body F-fluorodeoxyglucose (FDG) PET. Brain MRI (or head CT with IV contrast, if MRI is not applicable) is not required at screening if it has been performed within 8 weeks from C11-AMT imaging and was negative for parenchymal brain metastases or leptomeningeal disease. Tumor imaging requirements at screening may be adjusted to take into account the type of tumor imaging done before study enrollment (i.e. whole-body CT scan –chest, abdomen, and pelvis; add neck, if applicable- with IV contrast alone or whole body FDG PET coregistered with CT scan without IV contrast) in relation with timing of C11-AMT PET imaging or pembrolizumab initiation. See section 4.1 for details. Scans for disease assessment will be done at baseline and week 12 (or earlier if patient progresses). If patients continue to have clinical benefit (complete response, partial response, disease stability) after 12 months from pembrolizumab treatment they can continue to be imaged per standard of care.

CT scan of the chest abdomen and pelvis (add neck, if applicable) will be performed twice at baseline: (A) coregistered with FDG PET; in this case IV contrast will be administered, (B) coregistered with C11-AMT PET; in this case no IV contrast will be administered with CT and radiology report will be issued for clinical assessment of tumor burden.

Limited (i.e. not whole body; at least 1 bed position) scan will be performed as described in sections 4.1.1 and 4.1.2 and before fresh tumor biopsy.

Observer-rated toxicity will be assessed using the NCI-CTCAE v4.03

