## **6.7 Assessment of Efficacy**

Subjects who have completed C11-AMT PET, FDG PET and CT scan of the neck, chest, abdomen, and pelvis and have received at least 2 doses of pembrolizumab will be evaluable for assessment of response and progression. Subjects whose cancer growth is documented by physical examination without imaging confirmation will count as progression. Patients who end study therapy for any reason (e.g., toxicity of treatment, decide to withdraw) will still be followed for PFS and OS.

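### Section 4.4.2 takes patients who need a prohibited treatment out of the trial rather than off treatment, which can cost follow-up and a usable restaging CT

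*Combined protocol and SAP*

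**What the plan says.** Section 4.4.2 lists the treatments barred during screening and treatment: other anticancer drugs, investigational agents, live vaccines, most systemic steroids and most radiation. It exempts steroids for suspected immune events, short steroid courses of up to 7 days, and, at the investigator's discretion, radiation to a symptomatic solitary lesion or the brain. It then says that patients who "require the use of any of the aforementioned treatments for clinical management should be removed from the trial". Its last line is "There are no prohibited therapies during the Post-Treatment Follow-up Phase".

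The parent section, 4.4, gives a milder consequence: "discontinuation from trial therapy or vaccination may be required". Section 6.7 says "Patients who end study therapy for any reason (e.g., toxicity of treatment, decide to withdraw) will still be followed for PFS and OS", and 4.7 sets follow-up of up to 3 years after removal from study treatment. Section 4.9 treats leaving the study and leaving protocol therapy as different things.

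On the scan, the table in 6.1 marks FDG PET and the row "CT scan neck chest, abdomen/pelvis" in the End of Study Treatment column. Footnote 4 triggers that visit when "Patients permanently stop pembrolizumab for disease progression or investigator/patient preference", and 4.6 has nearly the same words ("Patients permanently stop study treatment for disease progression or investigator/patient preference"). Both set it 30 (±7) days after the last dose. Footnote 11 and 6.3.3 instead place the scan at week 12 (Day 1 of Cycle 5); footnote 11 allows it earlier only on progression.

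On evaluability, 6.7 asks for the two PET scans, CT and at least two doses. Section 8.1 adds a restaging contrast CT and attaches its two-infusion minimum to patients who progress before week 12.

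**The concern.** Sections 4.4 and 4.4.2 differ in scope (therapy against trial) and in force (may against should). Taken literally, 4.4.2 also contradicts the continued follow-up in 4.7 and 6.7. A site that obeys the sentence would stop collecting progression and survival data. It might also not do the End of Study Treatment scan, because that visit is tied to stopping treatment and no visit is tied to leaving the trial.

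The patients concerned are not a random sample. Someone who needs another anticancer drug, or radiation outside the exemption, before week 12 is less likely to be a responder. If that patient has no restaging CT, 8.1 leaves the patient out of the evaluable set and the ORR (secondary objective 2.2.1) loses a probable non-responder from its denominator. If the only CT was taken after the new therapy started, the plan does not say whether it measures response to pembrolizumab.

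**Working it through.** **1. The plan's own figure.** Inputs from 8.2: 10 responders, 13 non-responders, effect size 1.1 SD, one-sided 0.05, stated power 80%. The standard error of the mean difference is √(1/10 + 1/13) = 0.421 SD. A two-sample t-test (noncentral t, 10 + 13 − 2 = 21 degrees of freedom) gives power 81.2%, so the stated 80% is reproduced.

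**2. Who is already covered.** Take a patient who has not progressed, has had at least two doses, stops early and has a restaging contrast CT.
- 6.7: the dose minimum is met, with no condition about progression. Evaluable.
- 8.1: the condition about early progression qualifies only the dose minimum, and the scan may show response, stability or progression. Evaluable.

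This patient is scored by RECIST under the current text. Two cases remain: a patient with no restaging CT, and a patient whose only restaging CT follows the start of new anticancer therapy.

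**3. Can the scan come after new therapy?** With doses on days 0, 21 and 42 after the first dose, and week 12 at day 84:

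| Last dose | Visit day (±7) | Week | Days before week 12 |
|---|---|---|---|
| Dose 2 | 21 + 30 = 51 (44–58) | 7.3 (6.3–8.3) | 84 − 51 = 33 |
| Dose 3 | 42 + 30 = 72 (65–79) | 10.3 (9.3–11.3) | 84 − 72 = 12 |

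The visit leaves 23 to 37 days after the last dose in which a patient with an urgent need could start the next treatment. Nothing in 4.4.2, 4.6 or 6.1 requires the CT to come first.

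**4. Effect on the ORR.** Assume that the evaluable set is the planned 23 with 10 responders, and that k omitted patients are all true non-responders. Reported ORR = 10/23 = 43.5%. With them counted, ORR = 10/(23 + k):
- k = 1: 10/24 = 41.7%
- k = 2: 10/25 = 40.0%
- k = 4: 10/27 = 37.0%

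The last line assigns every one of the 27 − 23 = 4 non-evaluable patients to this cause. It is a ceiling and not an expectation.

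**5. Effect on the primary comparison.** Losses within the 27-to-23 allowance leave 10 against 13, so planned power stays at 81.2%. For losses beyond it, all non-responders:
- 10 against 12: standard error √(1/10 + 1/12) = 0.428, power 79.8%
- 10 against 11: standard error √(1/10 + 1/11) = 0.437, power 78.3%

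The comparison is of mean SUVmax within response groups. Losing some non-responders does not shift the expected non-responder mean unless, among non-responders, loss is related to SUVmax.

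**The case against.** The strongest reply is that the protocol read as a whole resolves the sentence. The parent section speaks of therapy, 4.4.2 itself ends by assuming a follow-up phase, and the protocol elsewhere uses removal from study loosely while contact continues: 4.7 for patients with unacceptable adverse events, and 5.1.8 for pregnant patients, who are then contacted at least monthly. This stands as evidence of intent. It does not change the operative instruction, and a site acts on that instruction.

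A reader might infer that every non-progressor stopped under 4.4.2 drops out of the 8.1 evaluable set. The documents do not support that: with two doses and a restaging CT the patient is evaluable. The End of Study Treatment scan is also a real safeguard, since stopping for a prohibited treatment can reasonably be read as investigator preference. In addition, 6.7 counts growth documented by physical examination as progression, although 8.1 still asks for a CT.

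The effect is also small. One patient moves the ORR by 43.5 − 41.7 = 1.8 points, against an exact 95% interval for 10/23 of about 23% to 66%, and the ORR has no test or decision rule. Section 8.2 attributes dropout to intolerance or rapid progression, at under 5% (0.05 × 27 = 1.35 patients). All of this stands.

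Finally, a blanket non-responder rule could do harm. It could bring in patients with a single dose, against the two-dose minimum in 4.2, 6.7 and 8.1, and could put misclassified patients into the SUVmax comparison. That is right, and it limits the remedy.

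**Conclusion.** The point holds as a wording conflict with a small consequence. Section 4.4.2 should say that patients stop study treatment, and the plan should cover the patient with no restaging CT and the one scanned only after new anticancer therapy. The ORR would be overstated by about 1.8 points for one omitted non-responder; larger figures need assumptions that no document supports. The size rests on two assumptions: how many patients are affected, which the documents do not give and which is probably few because most will already have progressed and been counted, and that those patients are non-responders.

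A reader might also infer that the primary result is biased or underpowered. The documents do not support that. Planned power is unchanged within the allowance for four non-evaluable patients, and the SUVmax contrast is biased only if loss depends on SUVmax, which nothing in the plan suggests. Confidence is medium, because intent probably matches the milder reading.

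**What to change.** **In 4.4.2:**
- Reword the sentence so that these patients are discontinued from study treatment, not taken out of the trial.
- State that follow-up under 6.7 continues unless consent is withdrawn.
- State that the End of Study Treatment restaging CT is done before any new anticancer therapy, including radiation, where feasible.

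**In 8.1, for the ORR estimate only:**
- Count as non-responders those patients with at least two doses who start new anticancer therapy before a documented response.
- Classify patients stopped only for steroids or a live vaccine by their restaging CT.
- Leave the primary SUVmax comparison on its present evaluable set.

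**Cost:** a few sentences and no added sample size. The downside is an occasional earlier scan and a slightly lower ORR.
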